#### 2.5.3. OUTCOME MEASURES

Primary outcome measures will be the sensitivity of pain and secondary outcome measures will be the ROM of flexion, flexion-extension and lateral flexion of the cervical spine, the endurance of the deep flexor muscles of the cervical spine, the respiratory function, the intensity as well as the sensory and affective dimensions of the pain, the functional capacity of the neck, the anxiety and depression, the fear of movement, the perception of fear and the attempt to avoid pain in relation to physical and work activities, the degree of destructive views about pain, the quality of life and patients' perceived change in their health conditions. Furthermore, the compliance rate will be recorded.

The measuring tools were selected based on their validity, reliability, ease of application and clinical economy. The outcome measures were assessed before the start as well as at the completion of the therapeutic interventions at five weeks, for both groups.

#### 2.5.3.1. PRIMARY OUTCOME MEASURE

#### 2.5.3.1.1. PAIN SENSITIVITY (PRESSURE ALGOMETER)

The primary outcome measure will be the pain sensitivity and a pressure algometer (Commander® Algometer, JTECH Medical, Midvale, Utah) will be used, measuring the Mechanical Pain Threshold (MPT). This model is a handheld algometer with two different heads (with surface of 0.5 cm^2, 1 cm^2), a flat pad and a fingertip adapter. The maximum input force reaches 111 N, while the wireless radio frequency (RF) reaches 2.4 GHz. The head which will be used has an area of one square centimeter (1cm^2) and the unit of measurement for the MPT value is kilogram per square centimeter (kg/cm^2).

In this PhD thesis, the recording of the pain sensitivity will be performed at specific points such as the upper part of the trapezius muscle and the suboccipital region, as the pressure algometer has shown high intra-rater reliability when applied to the upper trapezius muscle (Intraclass Correlation Coefficient / ICC: 0.85-0.86) and the suboccipital region (ICC: 0.84-0.93) in patients with chronic non-specific neck pain (Pérez-Martínez *et al.*, 2020). The measurement in the suboccipital region will be performed at the mastoid process and at the BL 10 point, which is located on the horizontal line that passes between the spinous processes of the C1 and C2 vertebrae and the oblique line that passes through the outer border of the upper part of the trapezius muscle. It is exactly 1 cm on either side of the vertical axis of the body, which passes through the spinous processes of the C1 and C2 vertebrae. In the upper trapezius muscle, the measurement point is between the midline and the lateral border of the acromion (Wang-Price *et al.*, 2019). In addition, measurements will be made at the zygopophyseal joint between C5-C6 intervertebral space (1/2

Cun), at the tibialis anterior muscle (Stomach 36/ST 36), at the middle part of the deltoid muscle (1-2 cm below the acromion) as well as in the levator scapula muscle (2 cm above its epiphysis, at the upper medial angle of the scapula) (Wang-Price *et al.*, 2019).

Patients will be placed in a prone position (Fischer, 1987) for all measurements. At each aforementioned point, three measurements will be taken with the possibility of a 30-second break between measurements (Pelfort *et al.*, 2015). The first measurement will be discarded since it will be considered as a trial. The average of the two consecutive measurements (second and third) will be calculated and recorded as the final value (Wilke *et al.*, 2014; Pelfort *et al.*, 2015). The force that will be applied for the measurements will be perpendicular to the body surface and the rate of pressure increase constant at 1 kg/cm^2 per second (Reeves *et al.*, 1986; Koo *et al.*, 2013), because if it is not constant the possibility of incorrect measurement will be increased.

#### 2.5.3.2. SECONDARY OUTCOME MEASURES

#### 2.5.3.2.1. CERVICAL RANGE OF MOTION (INERTIAL SENSOR)

Secondary measurements include range of motion (ROM) of flexion, flexionextension and lateral flexion of the cervical spine. It will be recorded using the Moover® 3D Inertial Motion Sensor (Sensor medica; Guidonia Montecelio, Roma, Italia). This device has dimensions 36×32×12mm and weight 15gr (including the battery), allows goniometric evaluation, acceleration and rotation and converts them into electrical signal. The accelerometer can record ROM and acceleration values in three axes (Thomas *et al.*, 2018). Through the software application, all recorded data are converted into diagrams and an automatic report is displayed. It has a 16bit resolution, automatic calibration, frequency up to 1000Hz, battery life of six hours and the connection is achieved via Bluetooth 3.0.

The Sensor will be positioned in the center of the forehead on the frontal bone at the level of the glabella, which is above the nasal bridge, and it will be fastened around the head with the assistance of a strap (Thomas et al., 2018). Then the rater will calibrate the device in a standardized neutral body position or starting position. The patients will be trained through standardized instructions using video-recorded movements and commands, to perform cervical movements (left-right rotation, left-right lateral flexion and flexion-extension) correctly. Patients will perform three full-ROM movements, in each plane of motion, pausing for one second at the end of the ROM. To avoid measurement errors due to trunk compensating movements, active stabilization of the trunk and the shoulders will be applied manually by the rater's hands placed over the distal clavicle and acromion region (Fletcher and Bandy, 2008) while sitting directly behind the subject and passive stabilization will be provided by the backrest of the chair. The validity and the reliability of the wearable motion sensors in cervical spine have been recorded in the literature (Anoro-Hervera *et al.*, 2019; Elizagaray-García *et al.*, 2021).

# 2.5.3.2.2. ENDURANCE OF THE DEEP CERVICAL FLEXORS MUSCLES (PRESSURE BIOFEEDBACK UNIT)

The endurance of the deep flexor muscles of the spine will be assessed with a pressure biofeedback unit (Chattanooga Stabilizer Pressure Biofeedback). It allows physical movements and especially those concerning the spine during exercise. The changing pressure will be recorded in an air-filled pressure cell, which is connected to a combined guide and plier. It is a device used for joint protection and stabilization exercises that contribute to the treatment and prevention of pain in the cervical spine or lumbar spine, while it also provides biofeedback to physical movements, reducing pain in these areas. The proportional pressure range is between 0 mmHg - 200 mmHg with an accuracy of +/–3mmHz (Chattanooga 2020). The efficiency index is calculated as the quotient where the numerator records the pressure increase in the chamber and the denominator the number of repetitions. The maximum applied pressure sustained for a period of ten seconds is defined as the degree of activation (Magee, 2018).

The craniocervical flexion test will be selected as it only evaluates the deep neck flexors and not the superficial flexor muscles (Strimpakos *et al.*, 2011). This test has intra- rater (ICC: 0.63) and inter- rater (ICC: 0.86) reliability in NSCNP patients. Moreover, there is significant correlation between craniocervical flexion test

and NDI (a = -0.40), SF36- Physical Component Summary/PCS (a = 0.56) and NRS (a = -0.37) (Jørgensen *et al.*, 2014).

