# 2.3. RESEARCH HYPOTHESISES

Two main research questions are formulated regarding the effectiveness of ATM versus a standard treatment regimen consisting of acupuncture and stretching, but also the effectiveness of ATM as monotherapy, which will be investigated through appropriate statistical controls. The formal basis of statistical tests is the null hypothesis under which there is no association between the exposure and the outcome (Killeen, 2005). Starting from the assumption of no relationship, statistical tests quantify the probability that the observed relationship was observed by chance, due to the random sampling distribution. When the null hypothesis cannot be rejected then the observed relationship is attributable to chance rather than a true effect of the exposure on the outcome (Banerjee *et al.*, 2009).

Thus, the null hypotheses to be tested are formulated as follows:

- Research question 1: Effectiveness of ATM (intervention group before the intervention vs. the same group after the intervention)
  - Null hypothesis H0A1: The application of ATM does not affect the pain sensitivity assessed by the Pain Pressure Threshold (PPT) measured

with the pressure algometer (Commander Algometer) in patients with chronic neck pain (main hypothesis).

- Null hypothesis H0A2: The application of ATM does not affect the cervical range of motion (ROM) recorded with the Moover threedimensional (3D) Inertial Motion sensor in patients with chronic neck pain (secondary hypothesis).
- Null hypothesis H0A3: The application of ATM does not affect the strength of deep neck flexor muscles as measured by the Chattanooga Stabilizer Pressure Biofeedback in patients with chronic pain in the cervical spine (secondary hypothesis).
- Null hypothesis H0A4: The application of ATM does not affect the respiratory function assessed by the portable spirometer (MIR Spirodoc) in patients with chronic neck pain (secondary hypothesis).
- Null hypothesis H0A5: The application of ATM does not affect the pain in the cervical spine in terms of its intensity and quality, i.e., its sensory, emotional and behavioral dimensions using the McGill Pain Questionnaire-short form (SFMPQ) in patients with chronic neck pain (secondary hypothesis).

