- Null hypothesis H0A6: The application of ATM does not affect the functionality recorded with the Neck Disability Index (NDI) in patients with chronic pain in the cervical spine (secondary hypothesis).
- Null hypothesis H0A7: The application of ATM does not affect the anxiety and depression captured by the Hospital Anxiety & Depression Scale (HADS) in patients with chronic neck pain (secondary hypothesis).
- Null hypothesis H0A8: The application of ATM does not affect the kinesiophobia as measured by the Tampa Scale Kinesiophobia (TSK\_GR) in patients with chronic neck pain (secondary hypothesis).
- Null hypothesis H0A9: The application of ATM does not affect the perception of the fear and the effort to avoid pain in relation to physical and work activities assessed by the Fear Avoidance Beliefs

Questionnaire\_Greek version (FABQ\_GR) in patients with chronic neck pain (secondary hypothesis).

- Null hypothesis H0A10: The application of ATM does not affect the degree of pain catastrophizing recorded by the Pain Catastrophizing Scale (PCS) in patients with chronic neck pain (secondary hypothesis).
- Null hypothesis H0A11: The application of ATM does not affect the quality of life as measured by the Short Form 12-item Health Survey (SF-12) in patients with chronic neck pain (secondary hypothesis).
- Research question 2: Effectiveness of ATM versus A-S
  - Null hypothesis H0B1: The effect of applying ATM does not differ in reducing the pain sensitivity (PPT) in patients with chronic neck pain from applying A-S (main hypothesis).
  - Null hypothesis H0B2: The effect of the application of ATM does not differ in the improvement of the cervical ROM in patients with chronic neck pain from the application of A-S (secondary hypothesis).
  - Null hypothesis H0B3: The effect of applying ATM does not differ in improving the strength of deep neck flexor muscles in patients with chronic neck pain than applying A-S (secondary hypothesis).
  - Null hypothesis H0B4: The effect of the application of ATM does not differ in the improvement of the respiratory function in patients with chronic neck pain from the application of A-S (secondary hypothesis).

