# 2.4. OBJECTIVE GOALS

Objectives of the study are summarized in the investigation of statistically significant differences in the outcomes of interest, i.e. in the measurements for pain sensitivity, intensity and quality (pressure algometer and SFMPQ), functionality (NDI), ROM (Moover 3D Inertial Motion sensor), endurance of deep neck flexor muscles (Chattanooga Stabilizer Pressure Biofeedback), respiratory function (portable spirometer) and psychological parameters (HADS, TSK, FABQ, PCS, SF-12). Differences in the outcomes of interest may arise:

a) between the start time (baseline) and the end time of the study within the A-ATM group (A-ATM group at baseline versus A-ATM group after the intervention).

b) between the compared groups of the clinical trial {group A ATM (Intervention Group) versus group B A-S (Active Control Group)}, both at the beginning of the study, as well as after the intervention.

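### The deep-neck-flexor index divides pressure by repetitions, so it is not monotone in performance and does not suit an endurance outcome; the plan also does not say whether it is the score analysed

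*Combined protocol and SAP*

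**What the plan says.** Section 2.5.3.2.2 opens with the construct: "The endurance of the deep flexor muscles of the spine will be assessed with a pressure biofeedback unit". It then describes two quantities obtained from the device.

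- An efficiency index, "calculated as the quotient where the numerator records the pressure increase in the chamber and the denominator the number of repetitions".
- A degree of activation: "The maximum applied pressure sustained for a period of ten seconds is defined as the degree of activation".

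The section gives no unit, pressure steps, repetition cap or scoring direction for the index, and does not say which quantity is analysed. It goes on to select the craniocervical flexion test and cites correlations of that test with disability (-0.40), physical health (0.56) and pain (-0.37).

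The hypotheses in section 2.3 use a different construct. H0A3 reads "The application of ATM does not affect the strength of deep neck flexor muscles as measured by the Chattanooga Stabilizer Pressure Biofeedback", and H0B3 begins "The effect of applying ATM does not differ in improving the strength of deep neck flexor muscles". The objectives in section 2.4 name "endurance of deep neck flexor muscles (Chattanooga Stabilizer Pressure Biofeedback". Strength appears in sections 2.3 and 2.8; endurance appears in sections 2.4, 2.5.3, 2.5.3.2.2, 2.10 and 2.12.

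The statistical analysis (section 2.9) covers scales and other indicators collectively, by linear mixed models with a group-by-measurement interaction. All p values are two-tailed at 0.05. Nothing there identifies the deep-neck-flexor variable.

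**The concern.** An endurance score should rise, or at least not fall, when a patient completes more repetitions at the same pressure. With repetitions in the denominator it falls. Section 2.10 promises a finding for each hypothesis, including whether ATM brings benefit and whether the active control does better, so the sign of the estimate will be interpreted. If the quotient is the analysed score, an arm that gained repetitions could be described as having deteriorated, or a real difference could vanish because gains in pressure and in repetitions offset each other. Because two quantities are defined and neither is chosen, a blinded analyst cannot tell from the plan which number tests H0A3 and H0B3, or which direction is improvement.

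**Working it through.** **Inputs.** The formula comes from section 2.5.3.2.2: index = P / R, where P is the pressure increase and R the number of repetitions. The plan gives no value, SD, target or worked example for this index, so there is no figure to reproduce. All values of P and R below are assumptions for illustration.

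**1. Equal pressure, more repetitions.** At P = 6 mmHg:

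| R | P / R |
|---|---|
| 2 | 3.0 |
| 3 | 2.0 |
| 5 | 1.2 |
| 10 | 0.6 |

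From 2 to 10 repetitions the index changes by (0.6 - 3.0) / 3.0 = -80%. For any fixed positive P, P / R falls as R rises, so the direction does not depend on the values chosen.

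**2. Both components change.** The index falls when R rises by a larger factor than P, ties when the factors are equal, and rises when P rises by the larger factor. Starting from 6/3 = 2.0:

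- 8/3 = 2.67 (higher)
- 8/4 = 2.0 (unchanged, although both components improved)
- 8/5 = 1.6 (lower, although both components improved)

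A patient at 2 mmHg with 1 repetition scores 2.0 and outranks one at 10 mmHg with 10 repetitions, who scores 1.0.

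**3. How often this happens on an assumed grid.** Take P in {2, 4, 6, 8, 10} mmHg and R from 1 to 10. Count every change in which neither component worsens and at least one improves.

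| Changes | Number | Index falls | Ties | Rises |
|---|---|---|---|---|
| All improvements | 775 | 436 (56%) | 28 (4%) | 311 (40%) |
| Same pressure, more repetitions | 225 | 225 | 0 | 0 |
| Both improve | 450 | 211 | 28 | 211 |

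The remaining 775 - 225 - 450 = 100 changes, with more pressure at the same repetitions, all raise the index. For comparison, the product P x R rises in all 775. The percentages describe the grid and do not predict patients.

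**4. Effect on the between-group estimate.** Suppose one arm moves from 6/3 to 6/5 and the other stays at 6/3. The changes are 1.2 - 2.0 = -0.8 and 0, so the interaction estimate is -0.8 against the arm that improved. With the product, the changes are 30 - 18 = +12 and 0.

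**5. Other readings of the text.**

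- *Numerator summed over repetitions.* The quotient is then mean pressure per repetition: (6 x 2)/2 = 6 and (6 x 10)/10 = 6. There is no reversal, but repetitions drop out.
- *Repetitions fixed by the test.* The quotient is then proportional to pressure. There is no reversal, but repetitions again carry no information.
- *Degree of activation is analysed.* This is one ten-second hold. There is no reversal and no repetition count.

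None of these readings gives credit for more repeated holds.

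**The case against.** The strongest reply is that the harm is conditional. The plan never says that the efficiency index tests H0A3 or H0B3. The index appears in a general description of the device, and the trial's own choice of test follows in the next paragraph. If the degree of activation is analysed, nothing reverses. The text also does not say that repetitions are those the patient achieves, nor does it exclude a summed numerator. All of this stands, and it is why the conclusion is worded with an if. It does not remove the point, because the section headed endurance contains a stated scoring rule that misbehaves on its plain reading, and the readings that avoid the reversal ignore repeated holds.

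Three stronger inferences are tempting and are not supported.

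- *That the direction of the hypotheses reverses.* H0A3 and H0B3 are non-directional and all tests are two-sided. Only the sign of the estimate and its interpretation can be wrong.
- *That better endurance always scores lower.* This holds at equal pressure, or when repetitions rise proportionally more than pressure. On the grid the index still rises in 311 of 775 improvements.
- *That the cited correlations show the quotient to be inverted.* They suggest that a higher score on the test is better, but the plan does not say which score the cited study used, so they cannot be tied to the quotient.

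The product is also not taken from the documents. It is one workable choice. The wording difference between strength and endurance is real but does not by itself show a reversal.

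**Conclusion.** The concern holds in a limited form. On its plain reading the efficiency index is not monotone in performance and is unsuitable as an endurance score. If it is the analysed variable, a real gain can be reported as a loss or as no change, and the wrong arm can be read as improved. Separately, and whichever reading is right, the plan does not name the analysed score and uses two construct names for one outcome.

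The fall at equal pressure follows from the formula alone, provided that repetitions are those achieved and the numerator is a single pressure rise. Its size in this trial cannot be stated, because the documents give no values; the -80% example and the grid counts are illustrative. This should be fixed before analysis, but it is not critical to the trial: it affects one secondary outcome, and neither the primary pressure pain threshold result nor the sample size rests on it.

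**What to change.** In section 2.5.3.2.2:

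1. Do not use the quotient as the analysed score.
2. Before analysis, name one variable for H0A3 and H0B3 whose value rises with performance. State its formula, its unit and that higher is better. For endurance, one example is pressure increase x number of repetitions, with a definition of which repetitions count.
3. Report the ten-second degree of activation separately.
4. Use one construct name for this outcome in sections 2.3 (H0A3, H0B3, H1A3, H1B3), 2.4, 2.5.3, 2.5.3.2.2, 2.8, 2.10 and 2.12.

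The cost is a few sentences and one derived variable. If pressure and repetitions are stored separately, the product can be computed from the same two raw values without re-measurement. The documents do not say whether they are, so the data collection form should be checked first. If only the quotient has been kept, the product cannot be recovered from it, and that should be stated as a limitation.

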#### 2.5.3.2.3. RESPIRATORY FUNCTION (SPIROMETER)

For the evaluation of the respiratory function, a portable spirometer of the MIR company (MIR Spirodoc), with dimensions of the central unit and the removable head-turbine 101x48x16mm and weight 99g and 46x47x24mm and weight 17g respectively, will be used. This measurement tool has an LCD touch screen, a rechargeable battery with a 30-hour reserve measurement, a built-in three-axis motion recorder (triaxial sensor-3D Oximeter®), while it can be connected to the computer either with USB 2.0 or Bluetooth® 2.1. It is indicated for applications in the field of rehabilitation, telemedicine and clinical research (Medical International Research 2020).

Portable spirometers are reliable compared to spirometry in a pulmonary function laboratory, which is considered as the gold standard. Additionally, has been found correlation between measurements performed in the pulmonary function laboratory and measurements done by the patient at home on the same day, regarding the FVC (ICC: 0.94) and FEV1 (ICC: 0.99) (Finkelstein *et al.*, 1993).

# 2.5.3.2.4. INTENSITY AND QUALITY OF PAIN (SHORT-FORM McGill PAIN QUESTIONNAIRE / SFMPQ)

Pain will also be assessed subjectively with the SFMPQ questionnaire which includes its intensity as well as its sensory and affective dimensions (Melzack 1987). It consists of 11 sensory and 4 affective descriptors of pain. The patient rates each description on a four-point Likert type intensity scale, where 0 – no pain, 1 – mild pain, 2 – moderate pain and 3 – severe pain. SFMPQ also includes a ten-point Visual Analogue Scale (VAS) and a six-point rating scale describing the present intensity of pain (PPI), where: 0=No pain, 1=Mild, 2 =Annoying, 3=Painful, 4=Horrible, 5=Unbearable. The total score amounts to 45 points -33 for the sensory subscale, 12 for the affective subscale, 10 for the VAS and 5 for the PPI- (Neurotoolkit 2020). Furthermore, the SFMPQ is comprehensible and can be completed by people of different educational levels (even primary school graduates). It is a tool for multidimensional assessment of pain in patients with chronic musculoskeletal problems (the research sample in the Greek population consisted of patients

experiencing chronic pain with spinal and osteoarthritic conditions) (Georgoudis *et al.*, 2000).

The short form of the questionnaire was translated and validated to the Greek population in 2000 by Georgoudis et al. (2000) (the GREEK-SMFPQ/the GR-SFMPQ). The internal reliability of the Greek version of the SFMPQ has been indicated (Cronbach's  $\alpha$  value = 0.71) (Georgoudis et al., 2000).

